9 STATISTICAL CONSIDERATIONS

The sections of the Statistical Considerations describe the statistical methods to be used to analyze the efficacy and safety. These methods may be revised and updated due to reasons such as regulatory requirements or need for further clarifications. The final analysis plan will be documented in a formal statistical analysis plan (SAP) that must be finalized before database lock. The SAP will include details on how variables will be derived, how missing data will be handled, and how censoring procedures will be applied to time to event related variables as well as the details on statistical methods to be used for safety and efficacy analyses. The final clinical study report will discuss deviations from the SAP, if any.

9.1 SAMPLE SIZE AND POWER

9.2 GENERAL ANALYSIS CONVENTION

Unless otherwise stated, all analyses will be performed using SAS Version 9.2 or higher and all hypothesis tests will be conducted at a two-sided significance level of 0.05.

Summary tabulations will display the number of observations, mean, standard deviation, median, minimum, maximum, and appropriate percentiles for continuous variables, and the number and percentage by category for categorical data. Summaries will present data by treatment arm and overall, if appropriate. The data listings will include all available efficacy and safety data.

In general, safety and efficacy data will be presented by histology type and overall.

9.3 ANALYSIS POPULATIONS

The safety population will include all enrolled patients who have received at least one dose of study treatment. The safety analyses will be based on this safety population.

The modified Intent-to-Treat (mITT) population will consist of all safety patient who have provided at least some post baseline efficacy assessments. The efficacy analyses will be based on this mITT population.

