	
indolent non-Hodgkin's lymphoma that is relapsed or refractory following at least one prior standard therapy regimen, without limit on prior therapies.
 
Enrollment
 
Following Screening, qualified patients will be administered TGR-1202 (umbralisib) monotherapy at 800 mg QD.
 
During the study period, all patients will be evaluated for response by CT, PET-CT and/or MRI every 3 cycles. For patients with WM without nodal involvement, response will be assessed by quantitative monoclonal IgM protein every 3 cycles. The best clinical response as well as disease progression will be determined by local investigator. Patients will remain on study treatment until the occurrence of definitive disease progression, unacceptable toxicity, or withdrawal from the study due to investigator decision or other reasons. Patients who discontinue from study treatment (either for toxicity or physician choice) and have not progressed will continue to be followed for progression. All enrolled subjects will be treated for at least 6 months, after which time the study may end.

Dosing Regimen (Cycle = 28 days)
	
TGR-1202 (umbralisib):
 
 • TGR-1202: Orally (800 mg) daily starting on Day 1 of Cycle 1.

Study Drugs
	
TGR-1202 is a highly specific and orally available PI3K delta (δ) inhibitor available in 200 mg tablets, supplied by TG Therapeutics, Inc.

Statistical Considerations
	
Sample Size: Up to 20 MZL patients and up to 20 WM patients may be enrolled in the study. The safety population will include all patients who take at least one dose of study medication. The safety analysis will be based on the safety population. The mITT (modified Intent to Treat) population will include all safety patients who have provided at least some post-baseline efficacy measures. The efficacy assessments will be based on the mITT population.
 
In general, the safety and efficacy data will be presented by histology type (MZL and WM) as well as combined.

LIST OF ABBREVIATIONS AND DEFINITIONS OF TERMS

Abbreviations and Definitions of Terms	
AE	Adverse Event
ALC	Absolute lymphocyte count
ALT	Alanine aminotransferase
AST	Aspartate aminotransferase
AUC	Area Under the Curve
BM	Bone Marrow
Ca	Calcium
CBC	Complete Blood Cell Count
Cl	Clearance
CLL	Chronic Lymphocytic Leukemia
cm	centimeter
Cmax	Maximum Concentration
CR	Complete Response
eCRF	Electronic Case Report Form
CRO	Contract Research Organization

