1.2.2 CLINICAL DEVELOPMENT OF TGR-1202

1.2.2.1 SINGLE-AGENT IN PATIENTS WITH RELAPSED OR REFRACTORY HEMATOLOGIC MALIGNANCIES

TGR-1202 was evaluated in a Phase I dose-escalation study in patients with relapsed and refractory hematologic malignancies (O'Connor et al, ASH 2015). As of the latest cutoff date for this study of December 2015, 81 patients were enrolled and eligible for safety evaluation, with 63 patients evaluable for efficacy. The median age was 65 years (range 22-85), 53/28 male and 14/81 enrolled patients had a diagnosis of DLBCL. Among all patients, the median number of prior therapies was 3 (range, 1-14), with 57% of patients having 3 or more prior therapies and 49% refractory to their immediate prior therapy.

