2.2 EFFICACY ENDPOINTS

Progression-free survival (PFS)

PFS is defined as the interval from Cycle 1/Day 1 to the earlier of the first documentation of definitive disease progression or death from any cause. Definitive disease progression based on revised response criteria for malignant lymphoma (Cheson et al, 2014 and Owen et al 2013).

Time to treatment failure (TTF)

TTF is defined as a composite endpoint measuring time from Cycle 1/Day 1 to discontinuation of treatment for any reason, including disease progression, treatment toxicity, and death.

Overall response rate (ORR)

ORR is defined as sum of CR and PR (and VGPR, MR for patients with WM) rates.

Duration of response (DOR)

DOR is defined as the interval from the first documentation of CR or PR or VGPR or MR to the earlier of the first documentation of definitive disease progression or death from any cause.

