4 STUDY DESIGN

4.1 OVERVIEW OF STUDY DESIGN

This study is designed as a Phase 2 trial to evaluate the efficacy and safety of TGR-1202 (umbralisib) monotherapy in previously treated non-follicular indolent non-Hodgkin's lymphoma. Patients are required to have non-follicular indolent non-Hodgkin's lymphoma that is relapsed or refractory following at least one prior standard therapy regimen.

Enrollment

Following Screening, qualified patients will be administered TGR-1202 monotherapy at 800 mg QD.

During the study period, all patients will be evaluated for response by CT, PET-CT and/or MRI every 3 cycles. For patients with WM without nodal involvement, response will be assessed by quantitative monoclonal IgM protein every 3 cycles. The best clinical response as well as disease progression will be determined by local investigator. Patients will remain on study treatment until the occurrence of definitive disease progression, unacceptable toxicity, or withdrawal from the study due to investigator decision or other reasons. Patients who discontinue from study treatment (either for toxicity or physician choice) and have not progressed should continue to be followed for progression every 6 months or per standard of care.

An independent DSMB will be established to advise the Sponsor on safety and ethical issues of the study. Once the database has been locked, the independent DSMB will review the primary and secondary efficacy analyses and safety data.

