8.4 DEFINITIONS OF TUMOR RESPONSE AND PROGRESSION

Evaluable for objective response. Only those patients who have had a pre-treatment baseline efficacy evaluation and at least one post-treatment efficacy evaluation will be considered evaluable for response. These patients will have their response classified according to the definitions stated below.

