9.8 EFFICACY ANALYSES

Each patient will be assigned to one of the following categories: 1) complete response, 2) partial response, 3) very good partial response, 4) minor response, 5) stable disease, 6) progressive disease, 7) early death from malignant disease, 8) early death from toxicity, 9) early death because of other cause, or 10) unknown (not assessable, insufficient data).

Many of the efficacy measures will be based on disease assessments. The best clinical response as well as disease progression will be determined by an independent central radiology group (ICRG) which will be blinded to treatment arm assignment. Definitive disease progression will be based on standard criteria (Cheson, B 2014 Lugano Classification; Appendix A -Criteria for Response Assessment and Owen et al 2013 Appendix B).

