9.9 MISSING VALUE HANDLING PROCEDURES

In general, other than for partial dates, missing data will not be imputed and will be treated as missing. The algorithms for imputation of partial dates vary depending upon the parameter and are presented in the Statistical Analysis Plan.

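### Efficacy is analysed only in treated patients with a post-baseline assessment, which can raise but never lower ORR and CR rate and discards early TTF events and deaths

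*Combined protocol and SAP*

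**What the plan says.** Section 9.3 defines the efficacy set: "The modified Intent-to-Treat (mITT) population will consist of all safety patient who have provided at least some post baseline efficacy assessments". It then assigns the efficacy analyses to that set. The synopsis (Statistical Considerations) has the same rule with slightly different wording: "The mITT (modified Intent to Treat) population will include all safety patients who have provided at least some post-baseline efficacy measures". Section 8.4 restricts response classification in a similar way: "Only those patients who have had a pre-treatment baseline efficacy evaluation and at least one post-treatment efficacy evaluation will be considered evaluable for response".

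On timing, Section 4.1 states that "all patients will be evaluated for response by CT, PET-CT and/or MRI every 3 cycles", and patients with WM without nodal disease have IgM measured at the same interval. Cycles last 28 days (Section 6.1).

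Section 9.8 assigns each patient to one of ten categories, the last four being "7) early death from malignant disease, 8) early death from toxicity, 9) early death because of other cause, or 10) unknown". Section 9.9 says that, partial dates apart, "missing data will not be imputed and will be treated as missing". Section 2.2 counts as a TTF event "discontinuation of treatment for any reason, including disease progression, treatment toxicity, and death", timed from Cycle 1/Day 1. PFS counts progression or death from any cause from the same origin.

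The documents state no all-treated efficacy analysis, and nothing says that the early-death and unknown categories count as non-response.

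**The concern.** Entry to the efficacy set depends on something that happens after treatment starts: staying in the study long enough to be assessed. Patients who do badly early are the least likely to meet that condition. ORR with its 95% confidence interval is the primary result of a single-arm study with at most 20 patients per histology, so each excluded patient moves the rate by 2 to 3 points or more, always in the drug's favour.

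TTF is affected most directly. It exists to count stopping for any reason, yet the rule deletes early stoppers who are never assessed. PFS loses deaths before any assessment, and any progression recorded without one. An unassessed patient who drops out alive contributes no PFS event either way.

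The sections also leave room for two denominators. Section 9.8 provides categories for early death and unassessable response, while Sections 8.4 and 9.3 remove most of the patients those categories would describe.

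**Working it through.** The plan gives no figure to reproduce here: no sample-size or power calculation is visible, and the expected share of unassessed patients is not stated.

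**Timing.** 3 cycles × 28 days = day 84 (week 12). The ±7-day window gives days 77 to 91.

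**Direction.** Let N be treated patients, r responders and d treated patients never assessed. No unassessed patient can be a responder, so the mITT rate is r/(N − d) and the all-treated rate is r/N. The first is at least as large as the second, with equality only if d = 0 or r = 0. The same holds for CR rate.

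**How many might be lost (assumption).** Two figures in the documents serve as rough proxies:
- 8% stopped for an adverse event in the integrated phase I analysis (synopsis, Study Rationale). 0.08 × 20 = 1.6 and 0.08 × 40 = 3.2. No timing is given, and some patients were on combination therapy.
- Section 1.2.2.1 reports "81 patients were enrolled and eligible for safety evaluation, with 63 patients evaluable for efficacy". (81 − 63)/81 = 18/81 = 22%; 0.222 × 20 = 4.4 and 0.222 × 40 = 8.9. The reasons are not given, and some patients may simply not have been assessed yet.

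**ORR, assuming 9 responders of 20 treated (exact Clopper-Pearson 95% CI).**

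| Dropped | Rate | 95% CI | Rise (points) |
|---|---|---|---|
| 0 | 9/20 = 45.0% | 23.1–68.5 | – |
| 1 | 9/19 = 47.4% | 24.4–71.1 | 2.4 |
| 2 | 9/18 = 50.0% | 26.0–74.0 | 5.0 |
| 3 | 9/17 = 52.9% | 27.8–77.0 | 7.9 |
| 4 | 9/16 = 56.25% | 29.9–80.2 | 11.25 |

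Both histologies combined: 18/40 = 45.0% (29.3–61.5) becomes 18/37 = 48.6% (31.9–65.6) with 3 dropped and 18/31 = 58.1% (39.1–75.5) with 9 dropped.

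A higher true rate makes the shift larger. 11/20 = 55.0% becomes 11/19 = 57.9% with 1 dropped and 11/16 = 68.75% with 4.

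**CR rate, assuming 2 CRs of 20.** 2/20 = 10.0%; 2/18 = 11.1%; 2/16 = 12.5%.

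**TTF at week 12.** Assume the d dropped patients are the only ones who stop by then. The all-treated failure-free share is 1 − d/20 = 95%, 90%, 85% or 80% for d = 1 to 4. The mITT set shows 100% each time.

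**Median TTF.** With the d earliest failures of 20 removed, the mITT median is the time at which a proportion q = 1 − 0.5(20 − d)/20 of all treated patients have failed: 0.525, 0.55, 0.575, 0.60. If TTF is exponential with no early censoring, the ratio to the true median is ln[1/(1 − q)]/ln 2 = 1.07, 1.15, 1.23, 1.32. The median is overstated by 7% to 32%.

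**The case against.** The best counter-argument is that few patients would be excluded. Sections 4.4 and 6.5 keep patients who stop without progression in follow-up, and once assessed they enter the mITT set with their TTF event. That stands: the rule removes only those never assessed. It also weakens the 8% proxy, since patients stopping for toxicity are among those followed. The 22% proxy comes from a dose-escalation study in mixed hematologic malignancies, whereas this disease is indolent. Nor is every exclusion a drug failure; Section 4.4 also lists withdrawn consent, pregnancy and sponsor discontinuation.

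A second argument is that the qualifying assessment is undefined, and a physical examination with B-symptoms at Cycle 2 Day 1 might count. The windows point the other way. Section 8 gives efficacy assessments during treatment ±7 days, matching tumor evaluations in the Section 5.1 schedule, while examinations in Cycles 2–6 have −3 days. If the broad reading were intended, the plan would need to say so.

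Third, Section 9.8 names no denominator, and its last four categories could be used inside the mITT set, for example for a death after a first assessment. The conflict is therefore implicit, but one reading must still be chosen.

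Fourth, Section 9 defers detail to a later SAP, Section 9.11 disclaims formal claims, and Section 9.4 reports population counts. Deferral does not undo a population already named, and bias in an estimate needs no hypothesis test. The counts would let a reader recompute ORR, but they do not restore the TTF and PFS curves, and the headline rate and interval would stay as reported. DOR is unaffected, because it uses responders only.

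**Conclusion.** The concern holds. Followed as written, the plan can raise but not lower ORR and CR rate, and it drops TTF events and pre-assessment deaths for patients never assessed. The direction is certain, because it follows from the definitions. The size is not: it depends on how many treated patients are never assessed, which the documents do not say.

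With 1 to 4 such patients in a histology group of 20 and a true ORR of 45%, the rate is overstated by about 2 to 11 points. For 40 combined, 3 to 9 such patients add about 4 to 13 points. The upper ends rest on the 22% proxy and are illustrations, not forecasts. The median TTF figures also require that those excluded are the earliest failures and that TTF is exponential without early censoring.

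**What to change.** - **Synopsis and Section 9.3:** make the safety (all-treated) population primary for ORR, CR rate, PFS and TTF.
- **Sections 9.8 and 9.9:** state that categories 7 to 10 stay in the denominator as non-responders.
- **Section 8.4:** reconcile the evaluability rule with 9.3 and 9.8 so that the plan gives one denominator.
- **Sensitivity analysis:** keep the mITT or evaluable analysis, labelled as such, and define which assessments qualify a patient for it.

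This needs changes of wording in the protocol and SAP and no extra data. The reported ORR may be slightly less favourable.

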9.4 PATIENT DISPOSITION

Patient disposition summaries will be presented by histology type and overall and will include the number of patients enrolled and the number and percentage of enrolled patients in the mITT and safety populations. The summaries will also include the reasons for permanent discontinuation of study treatment and study.

9.5 PATIENT DEMOGRAPHICS AND BASELINE CHARACTERISTICS

Baseline demographic and clinical characteristics will be summarized as percentages for categorical variables and as mean, standard deviation, median, minimum and maximum for continuous measures. The analyses of baseline characteristics will be performed for the mITT Population.

9.6 MEDICAL HISTORY

Medical history will be captured at the Screening visit. Medical history will be coded using MedDRA and will be summarized by MedDRA system organ class and preferred term for the Safety population.

9.7 EXTENT OF EXPOSURE

The dose (mg) of study drugs administered, the total number of doses of study drugs, and the duration of treatment (number of study cycles) will be summarized with descriptive statistics. The number and percentage of patients whose dose is modified at any time will be summarized by each type of modification by cycle and overall. The proportion of patients completing each cycle of treatment will be summarized.

9.8 EFFICACY ANALYSES

Each patient will be assigned to one of the following categories: 1) complete response, 2) partial response, 3) very good partial response, 4) minor response, 5) stable disease, 6) progressive disease, 7) early death from malignant disease, 8) early death from toxicity, 9) early death because of other cause, or 10) unknown (not assessable, insufficient data).

Many of the efficacy measures will be based on disease assessments. The best clinical response as well as disease progression will be determined by an independent central radiology group (ICRG) which will be blinded to treatment arm assignment. Definitive disease progression will be based on standard criteria (Cheson, B 2014 Lugano Classification; Appendix A -Criteria for Response Assessment and Owen et al 2013 Appendix B).

9.9 MISSING VALUE HANDLING PROCEDURES

In general, other than for partial dates, missing data will not be imputed and will be treated as missing. The algorithms for imputation of partial dates vary depending upon the parameter and are presented in the Statistical Analysis Plan.

9.10 STATISTICAL ANALYSES

9.10.1 PRIMARY EFFICACY VARIABLE

The primary efficacy outcome is Overall Response Rate (ORR). The ORR is defined as percent of patients who achieve CR or PR for MZL histology type patients and is defined as percent of patients

who achieve CR, VGPR, PR or MR for WM histology type patients. The estimated response rates as well as the two-sided 95% confidence interval of the response rate will be presented.

9.10.2 EFFICACY VARIABLE

The secondary efficacy variable will include:

- Complete Response (CR) rate;
- Progression free survival (PFS);
- Duration of response (DOR);
- Time to Treatment Failure (TTF).

These variables will be analyzed as appropriate.

9.11 MULTIPLE COMPARISON PROCEDURES

The study is a single treatment arm study. No formal claims will be made.

9.12 SAFETY ANALYSES

Safety evaluations will be based on the incidence, intensity, and type of adverse events, as well as on clinically significant changes in the patient's physical examination, vital signs, and clinical laboratory results. Safety analyses will be performed using the safety population. Exposure to study treatment and reasons for discontinuation of study treatment will also be tabulated.

9.13 ADVERSE EVENT CHARACTERISTICS

CTCAE term (AE description) and grade: The descriptions and grading scales found in the revised NCI Common Terminology Criteria for Adverse Events (CTCAE) version 4.0 will be utilized for AE reporting. All appropriate treatment areas should have access to a copy of the CTCAE version 4.0. A copy of the CTCAE version 4.0 can be downloaded from the CTEP web site http://ctep.cancer.gov/protocolDevelopment/electronic_applications/ctc.htm.

‘Expectedness’: AEs can be ‘Unexpected’ or ‘Expected’ for expedited reporting purposes only. Expected AEs are defined as those described in the TGR-1202(umbralisib) Investigator Brochure. Please refer to prescribing information for a listing of expected AEs.

9.14 DEFINITIONS OF ADVERSE EVENTS

An adverse event (AE) is any untoward medical occurrence in a patient or clinical investigation patient administered a pharmaceutical product. An AE does not necessarily have to have a causal relationship with this treatment. An adverse event (AE) can therefore be any unfavorable and unintended sign (including an abnormal laboratory finding, for example), symptom, or disease temporarily associated with the use of a medicinal product, whether or not considered related to the medicinal product. This includes any occurrence that is new in onset or aggravated in severity or frequency from the baseline condition.

In clinical studies, an AE can include an undesirable medical condition occurring at any time, including run-in or washout periods, even if no study treatment has been administered. The NCI Common Terminology Criteria for Adverse Events (CTCAE) v4.0 is to be used for the grading of severity of symptoms and abnormal findings. For adverse events not covered by the NCI-CTCAE Version 4.0 grading system, the following definitions will be used:

- **Grade 1:** Mild; asymptomatic or mild symptoms; clinical or diagnostic observations only; intervention not indicated.
- **Grade 2:** Moderate; minimal, local or non-invasive intervention indicated.
- **Grade 3:** Severe or medically significant but not immediately life-threatening; hospitalization or prolongation of hospitalization indicated.
- **Grade 4:** Life-threatening consequences; urgent intervention indicated.
- **Grade 5:** Death related to AE.

9.15 ADVERSE EVENTS (AE'S) AND TREATMENT EMERGENT ADVERSE EVENTS (TEAE'S)

All AEs and SAEs occurring on study will be listed by patient. The frequency and percentages of patients with treatment-emergent adverse events (TEAEs) will be tabulated by system organ class (SOC) and preferred term (PT), where treatment-emergent is defined as any AE that:

- Occurs after first dosing of study medication and through the end of the study or up through 30 days after the last dose of study treatment, or
- Is considered treatment-related regardless of the start date of the event, or
- Is present before first dosing of study medication but worsens in intensity or the investigator subsequently considers treatment-related.

TEAEs that are considered at least possibly related to study treatment will be tabulated as well as deaths, SAEs, and events resulting in treatment discontinuation.

AEs that occur after informed consent but before first dosing of study medication will not be summarized but will be listed.

At each level of summarization, a patient will be counted only once for each AE, SOC, or PT experienced within that level. In the summation for AE severity, within each level of AE, SOC, or PT experienced, the one with the highest severity will be included. In the summation for AE's relationship to the study drug, within each level of AE, SOC, or PT experienced, the one with the closest relationship to the study drug will be included.

